7.4 Evaluation at Completion of Study Intervention

Clinic Visit 4: 12 Weeks

11 weeks – 12 weeks and 2 days (77 – 86 days) after start of study agent

OR

Off-Agent Visit

- Prior to the visit
 - The participant will collect stool using the collection kit given to them during Clinic Visit 3.
- During the visit
 - Review vital signs, concomitant medications, and symptoms.
 - Physical exam may be performed when deemed appropriate by study team due to significant changes or medical events.
 - Obtain the following specimens:
 - One tube of urine (for optional future research)
 - One tube of stool (brought from home for fecal occult blood test)
 - Two tubes of blood (for clinical laboratory measurements): 1 green top for CMP and 1 purple top for CBC with differential.
 - Two tubes of blood (for research): 1 EDTA tube for plasma, white blood cell (WBC), red blood cell (RBC); 1 red top for serum.
 - Rectal swabs
 - Rectal biopsies
 - Collect unused study agent and participant diary and conduct a pill count.
- After the visit
 - Within 3 days after the visit, the research staff or nurse will telephone or email each participant to monitor for any adverse events due to biospecimen collection as well as compliance monitoring. Suggested statements for participant communications are provided in Appendix E.

7.5 Post-intervention Follow-up Period

Follow-Up Telephone or Email Contact

1 month after Clinic Visit 4 or Off-Agent Visit (± 7 days)

The research staff will telephone or email each participant to discuss the following:

- Any adverse events

7.6 Methods for Clinical Procedures

7.6.1 Rectal Swab and Biopsy Procedure

The procedure for collecting rectal swabs and biopsies will occur at Clinic Visits 2, 3 and 4. No fasting or bowel cleansing preparations is required. Participants are asked to try to have a bowel movement prior to arriving at clinic. If the participant was unable to clear his/her bowels, the procedure will still proceed. Participant is positioned in the Sims position. See section 10.2 for specimen collection information.

Patient monitoring

After the biopsy, the patient is monitored for thirty minutes. The study staff will check blood pressure and have the patient go to the restroom to check for bleeding prior to leaving the clinic. Patient is told that they can expect some blood on the tissue on the day of the biopsy. Bleeding heavier or more persistent than this should be reported. They should also report anal or lower abdominal pain, fever, a foul anal discharge, or anything else they think could be related to the biopsy. The gastroenterologists and the supporting medical team will handle emergencies. Any other problems discovered by the study team will be discussed at an appropriate level with the patient sufficient to affect referral to the patient's gastroenterologists or primary care physician who will also be informed if the participants agree in the informed consent form (i.e. the following questions will be added in the informed consent form: "If you develop a medical problem while on study, may we inform your physician? If yes, whom would you like us to inform?").

Any possible complications to the biopsies will be recorded on an Adverse Events Form; information will include a description of the complication, a rating of the severity, other essential information needed to evaluate the complication, an assessment of the likelihood that the event was due to a study procedure, and a statement of action taken. Minor problems after the procedure are handled in consultation with the gastroenterologist, and recorded in the subject's study file. If undue complications of biopsies or other procedures arise, the study will be stopped ahead of schedule. In addition, in the event of a severe or life-threatening complication, the Vanderbilt Cancer Center Clinical protocol Review Committee will be immediately notified, and an SAE submitted according to section 11.2. Patients will continue their usual care with the physician. Telephone numbers for the PI and study coordinator will be given to the participant. Emergencies will be handled by the gastroenterologist and supporting medical staff.

7.6.2 Stool Collection Procedure

Before the clinic visit, participants will receive a stool collection kit:

- Sterile stool container with wide mouth
- Zip-lock bags/ biohazard bags
- Insulated bag with ice packs
- Written and verbal instructions for collection of stool samples

Patients will be instructed to collect stool specimen. Collect the stool within 7 days prior to the clinic visit day.

- Place specimen in zip-lock bag / biohazard bag.
- Place zip-locked bag in insulated bag with ice pack.
- Store specimen in the refrigerator until ready to leave for clinic.
- Transport the sample to the clinic and give to study staff.

7.6.3 Research Blood Sample Collection Procedure

Research blood samples will be collected at all Clinic Visits. Blood (25 ml for each person) will be drawn into one EDTA tube for plasma, WBC, RBC and one red top tube for serum.

7.6.4 Urine Sample Collection

The urine samples will be collected Clinic Visits 1-4. Each urine sample will be collected in a sterile urine specimen container containing 100 mg ascorbic acid as a preservative. This sample will be transferred into 1.8ml cryovials.

8. CRITERIA FOR EVALUATION AND ENDPOINT DEFINITION

8.1 Primary Endpoint

BAX expression reflects earlier signaling of apoptosis and, thus, it is a more sensitive biomarker of apoptosis than TUNEL. Necroptosis is a newly described pathway for programmed cell death. To evaluate the effects of a 3-month intervention of continuous versus intermittent aspirin dosing (i.e. 325 mg daily and 325 mg 3 weeks on/3 weeks off), we chose the cell proliferation (i.e. Ki-67)/BAX ratio as a primary endpoint.

8.2 Secondary and Exploratory Endpoints

Immunohistochemistry (IHC)

Cell proliferation/TUNEL ratio, and cell proliferation/Necroptosis ratio will be secondary endpoints, whereas the expression of COX-2, BAX, TRPM7, joint index of COX-2 with TRPM7 and joint index of TRPM7 with BAX in rectal biopsy will be exploratory endpoints.

All biomarkers (TUNEL, pMLKL, COX-2, BAX, TRPM7 and Ki-67) will be detected by an established 6-plex mIHC/IF (multiplex immunofluorescent IHC) technique and analyzed quantitatively using a system composed of an Olympus BX-61 motorized microscope, X-Cite XYLIS Fluorescence Illuminator and imaging software (Q-Capture, ImageJ, CellProfiler). The imaging quantification will be conducted by a research pathologist and the detailed procedures for sequential mIHC/IF staining protocol, quality controls and automated image measurement pipelines are presented in the supplementary file. The final measures are generated automatically as “total positive cell count / total epithelial nuclei” for nuclear staining marker (Ki-67), or “total positive area / total epithelial cell area” for cytoplasmic/membranous staining markers (i.e. pMLKL, TRPM7, COX-2 and BAX). The COX-2 expression in both epithelium and stroma will be separately quantified using pan-CK for tissue segmentation. Quantitative results will be used for endpoints and semi-quantitative results will be used to validate quantitative results.

Fecal occult blood test

Fecal occult blood test will be used to monitor the safety of the treatment at each clinic visit.

Quantification of DNA methylation

Epigenetics, particularly aberrant DNA methylation in gene promoters (i.e. CpG methylation sites), play a critical role during CRC carcinogenesis^{55,56}. However, a very recent human study found that use of aspirin reduced the CpG methylation rates at colorectal carcinogenic genes (i.e. CDKN2A (cell cycle regulation), MGMT (DNA repair), DAPK1(apoptosis), CDH1(cell invasion), WNT16 (Wnt pathway) and RASSF1 (RAS signaling))⁵⁷.

We will extract high molecular weight genomic DNA from DBS samples with commercially available PureGene Kits (Gentra Systems, Minneapolis, MN). We will use the MethylationEPIC BeadChip to identify methylation biomarkers in candidate genes (i.e. CDKN2A (cell cycle regulation), MGMT (DNA repair), DAPK1(apoptosis), CDH1(cell invasion), WNT16 (Wnt pathway) and RASSF1 (RAS signaling)) involved in colorectal carcinogenesis, and other epigenome-wide methylation biomarkers in rectal biopsies..

Gut microbiota

Gut microbiota dysbiosis^{61,62}, particularly abundance of *E. coli* or *E. coli*-like bacteria^{63,64} and *Fusobacterium*⁶⁵⁻⁶⁸, was linked to CRC risk. We will evaluate the effects of aspirin on these bacteria and other microbiota in rectal swabs using whole-genome shotgun metagenomics (WGS) DNA sequencing.

8.3 Off-Agent Criteria

Participants may stop taking study agent for the following reasons:

- (1) Individuals who report minor upper GI symptoms such as dyspepsia, heartburn, dyspepsia, or heartburn who do not wish to remain on trial;
- (2) Inadequate agent supply;
- (3) Noncompliance (e.g. forget taking study agent);
- (4) Medical contraindication;
- (5) Concomitant medications.

Participants who go off-agent early will have an Off-Agent Visit (clinic visit 4 as listed in “7.1 schedule of events”) scheduled as soon as possible.

8.4 Off-Study Criteria

Accrual will be interrupted if at any time toxicity among participants requires withdrawal of 25% of participants based on the toxicity criteria outlined in Section 5.6. Toxicity will be reviewed by the NCI DCP Medical Monitor to determine whether accrual to the study should be permanently stopped.

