In addition to using aspirin every other day, as mentioned in the NCI TORFP BB-2015, previous animal studies have examined other intermittent dosing strategies in carcinogenesis models⁴⁰. Very recently, a DCP-sponsored rodent study found aspirin delivered on an intermittent schedule (i.e. 3 weeks on followed by 3 weeks off) had an equally high efficacy in preventing colon cancer with aspirin delivered continuously. This is a novel strategy. If confirmed in human studies, it may be able to minimize the adverse event and simultaneously maximize the high efficacy.

Apoptosis Mounting evidence from *in vitro*, *in vivo* and human studies indicates acquired resistance to apoptosis is one hallmark for almost all cancer types⁴¹. The maintenance of normal colorectal crypt architecture is based on the balance between the apoptosis at the base of crypts and the proliferation at the top⁴². *The transformation from normal colorectal epithelium to carcinoma is accompanied by a progressive resistance to apoptosis*⁴³. [name] group found in a prospective study that subjects with the highest tertile level of apoptosis in normal rectal mucosa had a 70% reduction in risk of future colorectal adenoma, compared to the lowest tertile level of apoptosis⁴⁴. Terminal deoxyribonucleotidyl transferase-mediated dUTP nick end labeling (TUNEL) and BAX expression⁴⁵ was used to measure apoptosis.

Biomarker for proliferation (Ki-67) Cell proliferation is another critical factor in tumorigenesis⁴⁶. As we mentioned earlier, the balance between apoptosis and proliferation maintains the normal colorectal crypt architecture⁴². Cell proliferation index has been used in many previous intervention trials to assess the effects of chemoprevention agents⁴⁷ while Ki-67 is one of the most frequently used natural proteins associated with proliferation⁴⁶. We have identified one published study which found aspirin treatment significantly reduced cell proliferation in young people with familial adenomatous polyposis compared to placebo arm⁴⁸.

Therefore, **we hypothesize** that 325 mg aspirin delivered 3 weeks on/3 weeks off has the same efficacy in increasing colorectal apoptosis, reducing colorectal cell proliferation and, in turn, decreasing cell proliferation/apoptosis ratio as aspirin delivered 325 mg daily, but confers reduced side-effect, i.e. gastrointestinal bleeding.

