3. SUMMARY OF STUDY PLAN

Design

Eligible participants for this intervention study will be colorectal adenoma patients diagnosed at Vanderbilt University Medical Center, with a three-arm Phase IIa randomized placebo-controlled trial design. The three arms include two treatment arms and one placebo arm. Treatment 1 will be 325 mg aspirin orally per day for 12 weeks. Treatment 2 will be 325 mg aspirin orally on an intermittent, “3-weeks active/3-weeks placebo” schedule for 3 months. We will randomize a total of 90 participants into two treatment arms with 40 participants per arm and placebo arm with 10 participants. We anticipate at least 72 participants will complete the study (with a 20% drop-out rate due to both non-compliance and adverse events); we are building in a higher attrition rate than our PPCCT trial of magnesium supplementation because we expect there will be more adverse events related to aspirin use than with magnesium supplementation.

Recruitment and Screening

Participants will be recruited from the Vanderbilt electronic medical records, and from the PPCCT recruitment pool. Study gastroenterologists will perform a medical chart review, and participants who are potentially eligible will be invited for Clinic Visit 1 (screening).

Clinic Visits

Clinic Visit 1: After the consent is signed, screening procedures are performed to determine eligibility, including blood, stool, and pregnancy tests. A medical history, concomitant medications review, and physical including vital signs and ECOG performance status will also be performed. An optional urine sample is collected for future research. Upon final determination of eligibility, the study team will submit the registration information through the study eCRF database. Participant will be randomized according to Section 6.8 procedures.

Clinic Visit 2 (within 6 weeks of Clinic Visit 1): Baseline tests are performed, including the Food Frequency Questionnaire and Baseline Clinic Visit Questionnaire, concomitant medications review, and vital signs. A blood and stool sample are collected for clinical monitoring. Baseline specimens collected include rectal swabs, and biopsies. Another optional urine sample is collected. Three bottles of study medication are dispensed.

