5.1 Dose Regimen and Dose Groups

The whole intervention period lasts for 12 weeks (range: 11 weeks – 12 weeks and 2 days):

Control Arm: Placebo (n=10)

Experimental Arm1: Aspirin 325 mg daily (n=40)

Experimental Arm2: Aspirin 325 mg 3 week ON/OFF (n=40). Individuals assigned to 325 mg aspirin 3-week on/3-week off will take placebo during 3-week off period.

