6.8 Registration/Randomization

In current study, there are three groups, two treatment groups (325 mg aspirin daily and 325 mg aspirin 3-week on/3-week off) and one control group. Individuals assigned to 325 mg aspirin 3-week on/3-week off will take placebo during 3-week off period.

This study will recruit 90 participants with colorectal adenoma. A permuted-block randomization design will be used to allocate the subjects into the treatment/placebo arm, and will be created by the study statistician. Both the subjects and the intervention administering staff will be blinded to assignments.

Procedures

1. A study coordinator must upload into the Northwestern Clinical Trials Management System, a signed and complete informed consent along with HIPAA authorization and a completed eligibility form for each participant identified as eligible to be entered into the study.
2. All participants must be registered in the Northwestern University Robert H. Lurie Comprehensive Cancer Center Clinical Trials Management System (CTMS). Participants must not start protocol treatment prior to registration in the Lurie Cancer Center CTMS.
3. After registration in the CTMS, participants will be assigned a participant identification number.
4. An NCPC Quality Assurance Monitor will submit the following into the REDCap Randomization Information Form: (1) Study Number, (2) Site, (3) Pharmacist Email(s), (4) Participant ID [PID], (5) Participant Initials, and (6) Randomization Date.
5. An Automatic Treatment Assignment Notification email will be sent to the research pharmacist(s) containing: (1) Study Number, (2) Site, (3) Participant ID [PID], (4) Participant Initials, (5) Randomization Date, and (6) Treatment Assignment.
6. The clinical research coordinator(s) will receive a Confirmation of Registration containing the PID via email.

The research pharmacist will dispense the study agent.

The following people will have a copy of the un-blinded randomization log: the study statistician at NU, the Quality Assurance Team at NU, and the Investigational Pharmacist at Vanderbilt. The following people will have access to the REDCap study project containing randomization information: the study statistician at NU and the Quality Assurance Team at NU. The study statistician will set up randomization blocks.

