11.1 Adverse Events

11.1.1 Reportable AEs

All AEs that occur after the informed consent is signed and baseline assessments are completed (including run-in) must be recorded on the AE CRF (paper and/or electronic) whether or not related to study agent.

11.1.2 AE Data Elements:

The following data elements are required for AE reporting.

- AE verbatim term
- NCI Common Terminology Criteria for Adverse Events version 4.0 (CTCAE v4.0) AE term (MedDRA lowest level term)
- CTCAE (MedDRA) System Organ Class (SOC)
- Event onset date and event ended date
- Treatment assignment code (TAC) at time of AE onset
- Severity grade
- Attribution to study agent (relatedness)

- Whether or not the event was reported as a SAE
- Whether or not the subject dropped due to the event
- Outcome of the event

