12.4 Data and Safety Monitoring Plan

A comprehensive Data Safety and Monitoring Plan has been submitted by Northwestern University, approved by the DCP, and is on file there. Any future changes will be forwarded for review.

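### The pooled 25% toxicity trigger in 8.4 can miss an excess confined to the daily aspirin arm; add a check within each aspirin arm

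*Combined protocol and SAP*

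**What the plan says.** Section 8.4 states: "Accrual will be interrupted if at any time toxicity among participants requires withdrawal of 25% of participants". The withdrawals that count are those required by 5.6. The consequence is a pause and a judgement: "Toxicity will be reviewed by the NCI DCP Medical Monitor to determine whether accrual to the study should be permanently stopped". The sentence names no arm, no base (randomised, dosed to date, or the planned 90) and no minimum number.

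The arms are 40 daily, 40 intermittent and 10 placebo (sections 3 and 13.1). On the intermittent arm, 5.1 says: "Individuals assigned to 325 mg aspirin 3-week on/3-week off will take placebo during 3-week off period". That is the same 325 mg dose for 6 of 12 weeks. Section 2.3 hypothesises that the intermittent schedule keeps efficacy "but confers reduced side-effect, i.e. gastrointestinal bleeding", and 13.1 repeats the expectation of fewer adverse events.

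Section 13.9 plans no interim analysis. On wider monitoring, 12.4 says: "A comprehensive Data Safety and Monitoring Plan has been submitted by Northwestern University, approved by the DCP, and is on file there". That plan is not reproduced.

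**The concern.** A pooled proportion is least sensitive when toxicity differs between arms, and this trial is built on the expectation that it does. If daily aspirin caused many non-serious withdrawals while the intermittent arm stayed close to placebo, up to 50 of the 90 participants in the denominator would come from arms with little toxicity. Accrual into the daily arm could then continue past a withdrawal rate well above 25% with no study-level review prompted by 8.4.

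**Working it through.** The plan gives no derivation or error rate for the 25%, so there is no figure to reproduce. The documents give no arm-specific withdrawal rates either. All rates below are assumptions, written daily/intermittent/placebo.

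**Counts on a fixed base of 90.** 0.25 × 90 = 22.5, so 23 withdrawals are needed. If all are in the daily arm, that is 23/40 = 57.5%. The daily rate that brings the pooled rate to 25% is (22.5 − 40 × intermittent rate − 10 × placebo rate)/40:

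- 5% and 5%: (22.5 − 2 − 0.5)/40 = 50%
- 10% and 5%: (22.5 − 4 − 0.5)/40 = 45%
- 15% and 5%: (22.5 − 6 − 0.5)/40 = 40%

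**Two cases that stay under the limit.** Halfway (20/20/5), 11/20 = 55% daily with none elsewhere is 11/45 = 24.4%. At full accrual, 16/40 = 40% daily plus 4/40 intermittent is 20/90 = 22.2%.

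**Fixed base, exact probability of at least 23 of 90.** 0.125 at 40/5/5%, 0.290 at 40/10/5%, 0.544 at 40/15/10% and 0.685 at 40/20/5%. By comparison, the probability of at least 10 of 40 in the daily arm at 40% is 0.984.

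**Running count, simulated.** Assumptions: permuted blocks of 9 (4:4:1; block size is not stated in the plan); 30 or 45 enrolled per year (from the year-1 range in 13.3); withdrawal time uniform over 12 weeks; withdrawn/started ≥ 0.25 checked at each enrolment and withdrawal until the 90th enrolment. The last column combines a pooled rule from 20 participants with a 25% check in each aspirin arm from 20 in that arm. Entries are the chance of a pause while accrual is open, and ranges span the two enrolment rates.

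| Assumed rates | As written | Pooled, minimum 20 | With within-arm check |
|---|---|---|---|
| 40/5/5% | 54–64% | 39–46% | 99% |
| 40/10/5% | 67–76% | 56–63% | 99% |
| 40/15/10% | 81–86% | 75–79% | 99% |
| 40/20/5% | 86–92% | 82–87% | 99% |
| 30/15/5% | 55–64% | 41–47% | 89–91% |

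Repeat runs widen the first entry to about 52–67%. In the 40% scenarios the rule as written fires at a median of only 7–12 enrolled, so part of its detection is small-number crossing.

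**Timing.** Scheduled on-treatment laboratory and stool tests fall at about weeks 9 and 12 (7.1). If all withdrawals surface then, the 40/5/5% figures are about 24–38% as written against 97–98% with the within-arm check.

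**Early crossing.** On a running count, 1/4 = 25% meets the limit. The chance of at least one withdrawal among the first four is 1 − 0.95⁴ = 18.5% at a 5% rate and 1 − 0.90⁴ = 34.4% at 10%. On a fixed base of 90 this does not arise.

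**Pauses when no arm truly reaches 25%** (uniform timing):

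| Assumed rates | As written | With within-arm check |
|---|---|---|
| 5% in all arms | 6–9% | under 1% |
| 10% in all arms | 14–21% | 9–10% |
| 20/10/5% | about 27–30% | about 45–49% |
| 20% in all arms | about 52–58% | about 70% |

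If withdrawals surface at weeks 9 and 12, the 10% row becomes about 2–8% as written against 6–8%.

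**The case against.** The strongest reply is that a pooled pause rule that preserves the blind is a legitimate choice in a 90-person Phase IIa trial of 325 mg aspirin, and that the Data and Safety Monitoring Plan may already contain arm-level review. The second part stands: the supplied documents cannot exclude it.

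The dilution scenarios are also assumed and some are extreme. Both aspirin arms take the same dose, and at 40/20/5% the rule as written already fires in 86–92% of trials. This stands as a limit on size. The problem is largest when intermittent toxicity is close to placebo, and 40/5/5% is near that worst case.

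Three stronger readings are tempting and are not supported:

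- A reader might infer that one early withdrawal will trip the rule. That holds only on a running count and only among the first four participants. The phrase about any time favours that reading but does not settle it. Nor can this defect be added to the fixed-base dilution figures, because they belong to different readings of the same sentence.
- A reader might infer that the within-arm package pauses less often than the current rule. That is so at common rates of 5–10% only if withdrawals are spread evenly. At 10% it reverses if they surface at weeks 9 and 12, and near 20% the package pauses more often.
- A reader might infer that participants are unprotected. The individual withdrawal rules in 5.6, notification of serious events within 24 hours (11.2.2) and the sponsor's right to discontinue (8.5) all operate regardless of 8.4.

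The blinding objection is also fair: 6.9 limits unblinding to medical necessity, so routine arm-level tallies should not go to the Medical Monitor.

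**Conclusion.** The point holds as a weakness of design. The pooled trigger can leave a large daily-arm excess unflagged on either a fixed or a running base, and a within-arm check detects it far more reliably: about 97–99% against 24–67% at 40/5/5%, across both timing assumptions. The gap narrows as intermittent toxicity rises.

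The exact size rests on assumed withdrawal rates, block size and withdrawal timing. The arithmetic of dilution does not.

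What is at stake is when accrual pauses for review. Dosing of those already enrolled and the primary analysis are not affected. Severity is minor to moderate, and the point falls away if the monitoring plan on file already provides an arm-level limit.

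**What to change.** In 8.4:

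1. State that the base is participants who have started study agent. Section 13.7 already counts toxicity from first dose but refers to aspirin, which does not fit the placebo arm.
2. Add a 25% check within each aspirin arm once 20 in that arm have started. The study statistician can keep the tally, since 6.8 says: "The following people will have a copy of the un-blinded randomization log: the study statistician at NU". The statistician tells the Medical Monitor only that the limit has been reached; any unblinding then follows 6.9.
3. If the Data and Safety Monitoring Plan already does this, cross-reference it instead.

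A minimum of 20 for the pooled rule is optional. It stops 1 of 4 from tripping a running count, but alone it lowers detection (39–46% against 54–64% at 40/5/5%), and its benefit depends on withdrawals coming early. The package figures above include it. Without it, every trial that pauses under the current rule would still pause, so pauses could only be more frequent than shown.

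The cost is wording and a running tally. Adverse event records (11.1.2) already hold "Treatment assignment code (TAC) at time of AE onset" and whether the participant dropped out because of the event. The main downside is more pauses when true rates are below but near 25%. For scale, section 3 plans "with a 20% drop-out rate due to both non-compliance and adverse events", so 20% for toxicity alone would use the whole allowance. The check also starts late: 20 per aspirin arm corresponds to about 20 × 9/4 = 45 enrolled.
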